6.2.1 Definition of unacceptable toxicity

GVHD will be graded as standard criteria and other toxicity will be graded as per NCI common toxicity criteria (v.4) (appendix I). Unacceptable toxicity is defined as any of the following related to the DLI procedure:

- (a) Grade $\geq III$ aGVHD of the gut or liver or Grade IV aGVHD of the skin lasting > 7 days;
- (b) Grade 4 toxicity from the procedure in the cardiac, dermatologic, gastrointestinal, hepatic, pulmonary, renal/genitourinary, or neurologic categories that lasts > 5 days;
- (c) Treatment-related death caused by the toxicities related to DLI procedure.

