4.53 DUK-CPG-001 transport and administration

Transport:

Study medications that are to be transported to another pharmacy in the hospital are transported by either a member of the Investigational Chemotherapy Service or by the Stem Cell Transplant Courier. If the medication is refrigerated or frozen, drug is transported with ice and immediately delivered to the appropriate satellite.

Administration:

Using standard institutional guidelines, 5.0 mg of DUK-CPG-001 will be injected intravenously right after the NK cell-enriched DLI. DUK-CPG-001 is expected to be stable within 4 hours of thaw.

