6.0 STUDY DESIGN AND ANALYSIS

This is a randomized, parallel phase II study of NK cell-enriched DLIs when administered alone or administered with the TLR9 agonist, DUK-CPG-001, from a 7-8/8 HLA-matched related/unrelated donor (Cohort A) or 4-6/8 HLA-matched related donor (Cohort B) following allogeneic stem cell transplantation.

In Cohort A, a total of 50 patients will be randomized with equal allocation to two arms defined by whether or not a TLR9 ligand, DUK-CPG-001, is administered with NK cell-enriched DLIs. In Cohort B, a total of 50 patients will be randomized with equal allocation to the two arms. Stratification will be done within disease types (myeloid or lymphoid diseases) in each cohort. A block randomized design is used to randomize patients to the two treatments within each stratum for each cohort. Primary endpoints are analyzed separately in Cohort A and B.

6.1 Primary Objectives 1 and 2

1. To evaluate the one-year progression-free survival rates in patients receiving NK cell-enriched DLI administered alone from a 4-6/8 HLA-matched related or 7-8/8 HLA-matched donor following allogeneic stem cell transplantation.
2. To evaluate the one-year progression-free survival rates in patients receiving NK cell-enriched DLI administered with a TLR9 ligand, DUK-CPG-001, from a 4-6/8 HLA-matched related or 7-8/8 HLA-matched donor following allogeneic stem cell transplantation

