A 2-stage MiniMax design will be used to test the null hypothesis that the progression-free survival rate is $\leq 34\%$ against the alternative hypothesis that it is $\geq 59\%$ in each arm. Twelve patients will be treated in the first stage. If the number of patients who are alive without relapse/progression is equal to 4 or less at 1 year after transplantation in one arm, then the study for the arm will be terminated and the treatment is ineffective. If there are at least 5 patients (42%) who are alive without relapse/progression at 1 year after transplantation, the sample size will be increased up to a maximum of 25 patients. If the number of patients who are alive without relapse/progression is equal to 12 or less at 1 year after transplantation, then the treatment is ineffective. If there are at least 13 patients (52%) who are alive without relapse/progression at 1 year after transplantation, this protocol will be deemed effective. This design has a significance level of 0.05, a power of 0.80, a probability of early termination under the null of 0.61, and an expected sample size under the null of 17 patients.

Table 5

Stage	Total Accrual	Close study/therapy if number of patients who are alive without relapse/progression is \leq
1	12	4 (33%)
2	25	12 (48%)

6.2 Primary Objective 3 and 4

3. To evaluate the rates of unacceptable toxicity of using NK cell-enriched DLI administered alone from a 7-8/8 HLA-matched related or unrelated donor or 4-6/8 HLA-matched related donor following allogeneic stem cell transplantation.
4. To evaluate the rates of unacceptable toxicity of using NK cell-enriched DLI administered with TLR9 ligand, DUK-CPG-001, from a 7-8/8 HLA-matched related or unrelated donor or 4-6/8 HLA-matched related donor following allogeneic stem cell transplantation.

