6.2.2 Statistical considerations

Rate of unacceptable toxicity will be calculated and monitored with the stopping rules based on 2-stage MiniMax design in the table below. For this early stopping rule, we will only include the rate of unacceptable toxicities from the first infusion. Some patients will receive the second planned DLI. If the rate of unacceptable toxicity for the second DLI exceeds these same boundaries as the first infusion, then the protocol will be amended to delete the plan for the second DLI. Toxicity in the other categories will be informally monitored and tabulated by Type and Grade, but they will not be used to determine tolerability of the procedure.

For purposes of toxicity monitoring, each patient will be followed for an unacceptable toxicity for 8 weeks after each NK cell-enriched DLI. Accrual will not be suspended while collecting data for the interim analyses. However, as soon as a boundary within a stage in the table above is crossed, the study will be closed to further accrual.

Patients will be stratified according to T cell depletion usage or not. Analysis within strata is not planned.

Cohort A (7-8/8 HLA-matched related or unrelated transplantation)

A 2-stage MiniMax design will be used to test the null hypothesis that the unacceptable toxicity rate is ≥ 0.40 against the alternative hypothesis that it is ≤ 0.15 in each arm. Seven patients will be treated in the first stage. If the number of patients with an unacceptable toxicity is equal to 3 or more at 16 weeks after the first NK cell enriched-DLI in one arm, then the study for the arm will be terminated. If there are at most 2 patients (29%) with an unacceptable toxicity at 16 weeks after the first NK cell enriched-DLI, the sample size will be increased up to a maximum of 20 patients. If the number of patients who are alive without relapse/progression is equal to 5 or more at 16 weeks after the first NK cell enriched-DLI, then the study for the arm will be terminated. If there are at most 4 patients (20%) with an unacceptable toxicity at 16 weeks after the first NK cell enriched-DLI, this protocol will be deemed safe and continue to accrue to a total of 25 patients. This design has a significance level of 0.05, a power of 0.80, a probability of early termination under the null of 0.58, and an expected sample size under the null of 12 patients.

Table 6

Stage	Total Accrual	Close study/therapy if number of patients with unacceptable toxicity is \geq
1	7	3 (43%)

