7.1 Adverse Events

An adverse event (AE) is any untoward medical occurrence in a subject receiving study drug and which does not necessarily have a causal relationship with this treatment. For this protocol, the definition of AE also includes worsening of any pre-existing medical condition. An AE can therefore be any unfavorable and unintended or worsening sign (including an abnormal laboratory finding), symptom, or disease temporally associated with the use of study drug, whether or not related to use of the study drug. Abnormal laboratory findings without clinical significance (based on the PI's judgment) should not be recorded as AEs. But laboratory value changes that require therapy or adjustment in prior therapy are considered adverse events.

From the time the subject is screened through the End of Study visit (as defined in Section 10.6), all AEs must be recorded in the subject medical record and adverse events case report form.

AEs will be assessed according to the CTCAE version 4.0. If CTCAE grading does not exist for an AE, the severity of the AE will be graded as mild (1), moderate (2), severe (3), life-threatening (4), or fatal (5).

Attribution of AEs will be indicated as follows:

- Definite: The AE is clearly related to the study drug
- Probably: The AE is likely related to the study drug
- Possible: The AE may be related to the study drug
- Unlikely: The AE is doubtfully related to the study drug
- Unrelated: The AE is clearly NOT related to the study drug

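### The unacceptable-toxicity definition names only the DLI procedure, so read literally a qualifying event attributed only to DUK-CPG-001 is not counted in the two combination arms

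*Combined protocol and SAP*

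**What the plan says.** Section 6.2.1 restricts the endpoint to the DLI three times. The lead-in reads "Unacceptable toxicity is defined as any of the following related to the DLI procedure". Limb (b) is "Grade 4 toxicity from the procedure in the cardiac, dermatologic, gastrointestinal, hepatic, pulmonary, renal/genitourinary, or neurologic categories", lasting more than 5 days. Limb (c) is "Treatment-related death caused by the toxicities related to DLI procedure". Limb (a), severe aGVHD, is governed by the lead-in. DUK-CPG-001 does not appear in the section.

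Objective 4, restated in section 6.2, is "To evaluate the rates of unacceptable toxicity of using NK cell-enriched DLI administered with TLR9 ligand, DUK-CPG-001". Section 6.0 has patients "randomized with equal allocation to two arms defined by whether or not a TLR9 ligand, DUK-CPG-001, is administered with NK cell-enriched DLIs", so each cohort has one combination arm. Section 6.2.2 applies the single definition to the two-stage tables in each arm, counts first-infusion toxicity only, and says of toxicity in other categories that "they will not be used to determine tolerability of the procedure".

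Section 4.53 describes a distinct administration: "5.0 mg of DUK-CPG-001 will be injected intravenously right after the NK cell-enriched DLI". Section 7.1 grades attribution against the study drug ("Definite: The AE is clearly related to the study drug"), a term it does not define.

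**The concern.** The endpoint and the objective have different scopes. Objective 4 concerns the combined regimen, whereas the definition that feeds its stopping rule concerns one component. The omitted component is the randomized one. The mismatch can only lower the count, and only in the combination arms.

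At stake are the two formal safety decisions in those arms: early termination, and the statement that the arm is safe. The stated significance level of 0.05 bounds the chance of passing a regimen whose true rate is at the null. That bound holds for the regimen only if every qualifying event it causes is counted.

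**Working it through.** **Does another section widen the definition?** None does.
- Sections 4.51 to 4.54 give DUK-CPG-001 its own preparation, storage, administration and adverse-effect text. The DLI has its own adverse-effect text in section 4.42.
- Section 4.6.1 speaks of the DLI with or without DUK-CPG-001, so there the word DLI does not include the agent.
- Section 7.1 records attribution to study drug and section 6.2.1 needs relation to the DLI procedure. Nothing links the two.

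**Inputs (section 6.2.2, Tables 6 and 7).**
- Cohort A: n1 = 7, stop at 3 or more; n = 20, safe at 4 or fewer; null 0.40, alternative 0.15.
- Cohort B: n1 = 9, stop at 4 or more; n = 23, safe at 6 or fewer; null 0.45, alternative 0.20.

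**Formulas.** Let X1 ~ Bin(n1, p), X2 ~ Bin(n − n1, p), r1 = the largest stage 1 count that continues, and r = the largest final count declared safe.
- P(safe) = Σ over x = 0..r1 of P(X1 = x) × P(X2 ≤ r − x)
- PET = P(X1 > r1)
- EN = n1 + (n − n1)(1 − PET)

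**The plan's own figures.**
- Cohort A at p = 0.40: 0.0280 × 0.3530 + 0.1306 × 0.1686 + 0.2613 × 0.0579 = 0.047. PET = 0.580. EN = 7 + 13 × 0.420 = 12.46. At p = 0.15, P(safe) = 0.804.
- Cohort B at p = 0.45: 0.0046 × 0.5461 + 0.0339 × 0.3373 + 0.1110 × 0.1672 + 0.2119 × 0.0632 = 0.046. PET = 0.639. EN = 9 + 14 × 0.361 = 14.06. At p = 0.20, P(safe) = 0.807.

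These agree with the stated 0.05, 0.80, 0.58 and 12 (A) and 0.05, 0.80, 0.64 and 14 (B). The designs are sound; the problem is what is counted.

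**Effect of not counting.** Hold the true rate at the null. Let d be the proportion of patients whose only qualifying event is attributed to DUK-CPG-001 alone. The rule then sees p0 − d. The documents give no value for d, so it is varied.

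| Uncounted d | A: rate seen | A: P(safe) | A: PET | B: rate seen | B: P(safe) | B: PET |
|---|---|---|---|---|---|---|
| 0 | 0.40 | 0.047 | 0.58 | 0.45 | 0.046 | 0.64 |
| 0.01 | 0.39 | 0.056 | 0.56 | 0.44 | 0.056 | 0.62 |
| 0.02 | 0.38 | 0.067 | 0.54 | 0.43 | 0.067 | 0.59 |
| 0.03 | 0.37 | 0.080 | 0.51 | 0.42 | 0.080 | 0.57 |
| 0.05 | 0.35 | 0.110 | 0.47 | 0.40 | 0.113 | 0.52 |
| a quarter of p0 | 0.30 | 0.222 | 0.35 | 0.3375 | 0.272 | 0.36 |

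In the last row d is 0.40 × 0.25 = 0.10 in A and 0.45 × 0.25 = 0.1125 in B.

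**Which values of d are plausible?** Limb (a) is aGVHD after a donor-cell infusion, which is hard to attribute to DUK-CPG-001 alone, so the gap lies mainly in limbs (b) and (c). Table 3A (section 4.54) lists grade 3/4 events with the identical agent as monotherapy. No single entry in a limb (b) organ class exceeds 9% (dyspnea, 2 of 23). The table pools grades 3 and 4 and has no duration condition, while limb (b) needs grade 4 for more than 5 days. It also lists events singly, so it gives no patient-level rate. It points to the upper rows of the table above without fixing a value.

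**The case against.** The strongest reply is that the DLI procedure may mean the whole treatment session. Objective 4 stands just above the definition and names the regimen, section 4.4 treats infusion and injection under one plan, the injection follows the cells directly, and limb (c) opens with treatment-related death. Investigators may also be unable to separate two products given so close together. This stands in part: the wording is ambiguous, and an investigator could count such events. But the broad reading is written nowhere, and the separate handling in section 4 points the other way. If it was intended, the amendment only records it.

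Other safeguards exist. Section 7.2.1 covers reporting of serious, unexpected reactions at least possibly related to the study, section 4.3.3 follows grade 3 or greater toxicity due to the study, and section 7.4 provides annual committee review. They limit harm, but they do not feed the boundary.

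A reader might infer three stronger points that the documents do not support:
- *That section 7.1 offers no way to attribute an event to the DLI.* The scale applies to all subjects, including those given cells alone, so study drug may well include the cells. The term is undefined; a missing category is not shown.
- *That half of all events could go uncounted, giving P(safe) of 0.60 in A and 0.72 in B.* That needs 20 and 22.5 percentage points attributed to DUK-CPG-001 alone, which neither the aGVHD limb nor Table 3A supports.
- *That a planned comparison of toxicity between arms is spoiled.* None is planned; each arm is tested against a fixed null.

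**Conclusion.** The concern holds as a defect of wording in the primary safety endpoint. Applied literally, section 6.2.1 does not measure objective 4, and the stopping rule can pass a combination arm that it should not. The direction is certain on that reading; the size is not. One to 5 uncounted percentage points raise the chance of a wrong safe declaration from just under 0.05 to between 0.056 and about 0.11 in each cohort. The 0.22 and 0.27 of the quarter-uncounted case are an extreme. These figures assume a true rate exactly at the null, independent patients and the boundaries as printed. The DLI-only arms and the arithmetic of the two-stage designs are not affected.

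**What to change.** In section 6.2.1, replace the references to the DLI procedure (lead-in and limb (c)) and to the procedure (limb (b)) with *related to the NK cell-enriched DLI and/or DUK-CPG-001*, for the endpoint and stopping rule. Keep the boundaries in Tables 6 and 7 and the present relatedness threshold. A move to *at least possibly related* would change the endpoint in all four arms and needs its own justification. In section 7.1, state that study drug covers both the NK cell-enriched DLI and DUK-CPG-001, so that the endpoint can be derived in every arm.

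Section 4.4.1 and footnote 5 of the Appendix V schedule refer to section 6.2.1 when deciding on the second DLI, with a relatedness qualifier of their own. The sponsor must reconcile those passages with the revised definition. This review takes no position on what that treatment rule should be.

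The cost is a short amendment and a combination arm that reaches a boundary somewhat more often. Suppose the DLI-attributed rate is at the design alternative and DUK-CPG-001 independently adds 5% (an assumption). The totals are 1 − 0.85 × 0.95 = 0.1925 in A and 1 − 0.80 × 0.95 = 0.24 in B. P(safe) is then 0.634 instead of 0.804 in A, and 0.658 instead of 0.807 in B. That is the rule responding to the toxicity of the regimen actually given. Sample size is unchanged.

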6.2.2 Statistical considerations

Rate of unacceptable toxicity will be calculated and monitored with the stopping rules based on 2-stage MiniMax design in the table below. For this early stopping rule, we will only include the rate of unacceptable toxicities from the first infusion. Some patients will receive the second planned DLI. If the rate of unacceptable toxicity for the second DLI exceeds these same boundaries as the first infusion, then the protocol will be amended to delete the plan for the second DLI. Toxicity in the other categories will be informally monitored and tabulated by Type and Grade, but they will not be used to determine tolerability of the procedure.

For purposes of toxicity monitoring, each patient will be followed for an unacceptable toxicity for 8 weeks after each NK cell-enriched DLI. Accrual will not be suspended while collecting data for the interim analyses. However, as soon as a boundary within a stage in the table above is crossed, the study will be closed to further accrual.

Patients will be stratified according to T cell depletion usage or not. Analysis within strata is not planned.

Cohort A (7-8/8 HLA-matched related or unrelated transplantation)

A 2-stage MiniMax design will be used to test the null hypothesis that the unacceptable toxicity rate is ≥ 0.40 against the alternative hypothesis that it is ≤ 0.15 in each arm. Seven patients will be treated in the first stage. If the number of patients with an unacceptable toxicity is equal to 3 or more at 16 weeks after the first NK cell enriched-DLI in one arm, then the study for the arm will be terminated. If there are at most 2 patients (29%) with an unacceptable toxicity at 16 weeks after the first NK cell enriched-DLI, the sample size will be increased up to a maximum of 20 patients. If the number of patients who are alive without relapse/progression is equal to 5 or more at 16 weeks after the first NK cell enriched-DLI, then the study for the arm will be terminated. If there are at most 4 patients (20%) with an unacceptable toxicity at 16 weeks after the first NK cell enriched-DLI, this protocol will be deemed safe and continue to accrue to a total of 25 patients. This design has a significance level of 0.05, a power of 0.80, a probability of early termination under the null of 0.58, and an expected sample size under the null of 12 patients.

Table 6

Stage	Total Accrual	Close study/therapy if number of patients with unacceptable toxicity is \geq
1	7	3 (43%)
2	20	5 (25%)

Cohort B (4-6/8 HLA-matched related transplantation)

A 2-stage MiniMax design will be used to test the null hypothesis that the unacceptable toxicity rate is ≥ 0.45 against the alternative hypothesis that it is ≤ 0.20 in each arm. Nine patients will be treated in the first stage. If the number of patients with an unacceptable toxicity is equal to 4 or more at 16 weeks after the first NK cell enriched-DLI in one arm, then the study for the arm will be terminated. If there are at most 3 patients (33%) with an unacceptable toxicity at 16 weeks after the first NK cell enriched-DLI, the sample size will be increased up to a maximum of 23 patients. If the number of patients who are alive without relapse/progression is equal to 7 or more at 16 weeks after the first NK cell enriched-DLI, then the study for the arm will be terminated. If there are at most 6 patients (26%) with an unacceptable toxicity at 16 weeks after the first NK cell enriched-DLI, this protocol will be deemed safe and continue to accrue to a total of 25 patients. This design has a significance level of 0.05, a power of 0.80, a probability of early termination under the null of 0.64, and an expected sample size under the null of 14 patients.

Table 7

Stage	Total Accrual	Close study/therapy if number of patients with unacceptable toxicity is \geq
1	9	4 (44%)
2	23	7 (30%)

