4.4 Patient NK cell infusion and CpG administration plan

This treatment regimen may be administered on an outpatient basis.

4.4.1 NK cell-enriched DLI:

The target cell dose for NK cell-enriched DLI will be as many cells as can be collected with less than 0.5×10^6 CD3+ CD56- cells/kg patient weight in the 4-6/8 HLA-matched related setting and 1×10^6 CD3+ CD56- cells/kg patient weight in the 7-8/8 HLA-matched related or unrelated setting. The first NK cell-enriched DLI will be administered between one to six months post-transplant. The second NK cell-enriched DLI will be administered one to three months post the first infusion, in patients who have < grade II aGVHD at the time of infusion and have not had unacceptable toxicities (see 6.2.1 Definition of unacceptable toxicity) that are at least possibly related to the previous DLI and resolved to grade 1 or less. The second DLI will NOT be administered in patient with \geq grade III aGVHD at the time of infusion or unacceptable toxicities at least possibly related to the first infusion. If patients have GVHD and were on immunosuppressive therapy at study entry, patients will continue on their stable dose of immunosuppressive agents started for therapy of acute GVHD before the NK cell-enriched DLI, and will not taper until at least 6 weeks following the each NK cell-enriched DLI (unless disease progression or patient toxicity from the agents requires earlier taper). The donor NK cells will be infused over 30 minutes. Diphenhydramine 25 mg iv or po, and Acetaminophen 650 mg po will be used prior to each reinfusion, unless there is a history of allergy or contraindication in the patient, in which case hydrocortisone 50mg IV will be used.

These cells are infused into the patient via a peripheral intravenous line or central line. If signs of GVHD occur after NK cell-enriched DLI, immunosuppressive agents (prednisone, cyclosporine, tacrolimus and/ or mycophenolate preferred first choices) may be started.

4.42 Adverse effect of NK cell-enriched DLI:

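### The toxicity test in section 6.2.2 covers the first infusion only, but passing it declares a protocol of up to two DLIs safe

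*Combined protocol and SAP*

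**What the plan says.** Section 4.4.1 plans two infusions: "The second NK cell-enriched DLI will be administered one to three months post the first infusion". A patient with "unacceptable toxicities at least possibly related to the first infusion" does not get the second. Primary objectives 3 and 4 concern the unacceptable-toxicity rate of the DLI treatment, alone or with DUK-CPG-001, and are not limited to the first infusion.

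Section 6.2.2 then sets these rules for each arm:

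- **Events counted:** "For this early stopping rule, we will only include the rate of unacceptable toxicities from the first infusion".
- **Second infusion:** "Some patients will receive the second planned DLI". The trigger is worded "If the rate of unacceptable toxicity for the second DLI exceeds these same boundaries as the first infusion", and the consequence is an amendment that drops the second DLI.
- **Window:** "each patient will be followed for an unacceptable toxicity for 8 weeks after each NK cell-enriched DLI". The decision sentences, by contrast, count patients at 16 weeks after the first DLI.
- **Cohort A:** the null is a rate of at least 0.40 and the alternative at most 0.15. Stop at 3 of 7, then at 5 of 20.
- **Cohort B:** null 0.45, alternative 0.20. Stop at 4 of 9, then at 7 of 23.
- **Conclusion on passing:** "this protocol will be deemed safe and continue to accrue to a total of 25 patients".

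Each design is stated to have a significance level of 0.05 and a power of 0.80.

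**The concern.** The conclusion is about the protocol, but the count behind it is limited to the first of two planned exposures. Because a related unacceptable toxicity after the first DLI rules out the second, first- and second-infusion events fall in different patients, so their counts add up. Two rates that are each tolerable can sum to a per-patient rate at the level the design calls unacceptable, and no rule looks at that sum. At stake is what may be claimed at the end: an error rate derived for one infusion would be read as the chance of wrongly clearing the two-infusion treatment.

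**Working it through.** **1. Reproduce the stated designs.** P(pass | p) = Σ over x ≤ c1 of Bin(x; n1, p) × P(X2 ≤ c − x), with X2 ~ Bin(n − n1, p). The stage-2 stopping sentences in 6.2.2 name patients alive without relapse, so the toxicity boundaries of Tables 6 and 7 are used.

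- A (n1 = 7, c1 = 2, n = 20, c = 4) at p = 0.40: 0.0280 × 0.3530 + 0.1306 × 0.1686 + 0.2613 × 0.0579 = 0.047. At p = 0.15: 0.804. Early termination under the null: 0.580.
- B (9, 3, 23, 6) at p = 0.45: 0.046. At p = 0.20: 0.807. Early termination: 0.639.

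These agree with the plan, so for one infusion the design is correct.

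**2. Translate to a per-patient rate.** Assume the same independent risk p at each infusion, and that a share f of patients free of first-infusion toxicity gets the second. Then the per-patient rate is p + (1 − p)·f·p. The documents give neither f nor the second-infusion risk, so f = 0.5 to 1.0 is shown. Solve for the p that puts the per-patient rate at the null, then apply the formula in step 1.

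| f | A: p | A: P(pass) | B: p | B: P(pass) |
|---|---|---|---|---|
| 0.5 | 0.296 | 0.23 | 0.338 | 0.27 |
| 0.7 | 0.264 | 0.34 | 0.302 | 0.40 |
| 1.0 | 0.225 | 0.49 | 0.258 | 0.58 |

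For example, A at f = 0.7: 0.1170 × 0.7575 + 0.2937 × 0.5374 + 0.3161 × 0.2919 = 0.339.

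**3. Add the second-DLI check (simulation, f = 0.5 to 1.0).** The result depends on how the boundary is read.

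| Reading of the second-DLI boundary | A | B |
|---|---|---|
| Rate below 25% / 30% of recipients, final look only | 0.09–0.29 | 0.12–0.41 |
| Same, plus a stage-1 look at the first 7 / 9 recipients | 0.09–0.27 | 0.12–0.38 |
| Raw count, fewer than 5 / 7 patients | 0.21–0.31 | 0.26–0.46 |

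**4. Let the 16-week count govern instead.** Assume second-DLI timing uniform over 1–3 months and toxicity onset uniform over the 8 weeks after it. About 82% of second-DLI events then fall inside 16 weeks. Counting them with the first-infusion events, P(pass) is 0.07–0.08 (A) and 0.07–0.09 (B).

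**5. Test the obvious remedy.** Apply 5/20 and 7/23 unchanged to patients with toxicity after either DLI, at the alternative rate per infusion and f = 0.7.

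- A: per-patient rate 0.15 + 0.85 × 0.7 × 0.15 = 0.239. P(pass) falls from 0.80 to 0.43 (0.46 with the final boundary alone).
- B: 0.20 + 0.80 × 0.7 × 0.20 = 0.312. P(pass) falls from 0.81 to 0.36 (0.39 with the final boundary alone).

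**The case against.** **The 16-week count may already cover both infusions.** The first-infusion sentence is worded for the early stopping rule, and the decision sentences do not repeat the limit. On that reading the gap nearly closes (step 4). This stands as far as it goes, so a reader may not infer that the problem exists whichever window applies. But the plan does not say that the 16-week count overrides the first-infusion sentence. Even if it did, a second DLI given at about 13 weeks would have only about 3 of its 8 weeks counted.

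**The nulls may be meant per infusion.** The plan never calls "0.40 against the alternative hypothesis" a per-patient rate over both DLIs. Taken per infusion, 0.05 is right, and a separate check that can remove the second DLI is an openly stated choice. This also stands: the stated error rates are not miscalculated. What does not follow from them is a conclusion about the whole protocol.

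**The second-DLI check protects patients.** It does in part. A reader might infer that 4 + 4 of 20 (40%) in A or 6 + 6 of 23 (52%) in B would cross no boundary. That needs a raw-count reading, and the text says rate. After 4 first-infusion events in A, at most 16 patients remain. To stay below 25%, at most 3 of 16 may have toxicity, a total of 7/20 = 35%. In B, at most 5 of 17 (29%) keeps the rate below 30%, a total of 11/23 = 48%. With about 11 and 12 recipients, as at f = 0.7, the largest passing totals are 6/20 = 30% and 9/23 = 39%. The documents therefore do not support the claim that an observed 40–52% passes every rule.

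**Equal risk is doubtful.** Recipients of the second DLI are selected for having tolerated the first. If their risk is lower, the probabilities in step 2 fall towards 0.05. For the first-infusion test only the product of uptake and relative risk matters, so the f = 0.5 row also represents full uptake at half the risk.

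**Conclusion.** The point holds as a mismatch between the test and its conclusion. With the first-infusion sentence in force, 0.05 and 0.80 belong to a single infusion, and no rule assesses patients harmed by either. With a true per-patient rate at the null, equal independent risk and 50–100% uptake, the first-infusion test passes with probability 0.23–0.49 (A) and 0.27–0.58 (B). With the second-DLI check read as a rate, both are passed with probability about 0.09–0.29 and 0.12–0.41, and with higher probability if it is read as a raw count. All exceed 0.05, but their size rests on assumptions that the documents do not supply. If the 16-week count governed, about 0.07–0.09 would remain. The plan should be changed, mainly because it leaves open which of these readings applies.

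**What to change.** In section 6.2.2:

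1. Reconcile the first-infusion sentence, the 8-week window and the 16-week count, and say to which infusion an event after both DLIs is assigned.
2. State whether the second-DLI boundary is a count or a rate, and give its denominator.
3. If the first-infusion count is kept, word the conclusion as the first infusion being deemed safe, and say that 0.05 and 0.80 apply to that only.
4. Report for each arm the proportion of patients with an unacceptable toxicity after either DLI, followed to 8 weeks after that patient's last DLI, with an exact confidence interval.

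This needs no additional follow-up, since 8 weeks are already planned after each DLI. The cost is a narrower safety claim. Do not carry 5/20 and 7/23 over unchanged to either-DLI events: step 5 shows that a treatment at the alternative rate per infusion would then usually fail. A formal per-patient test would need its null and alternative restated and its boundaries re-derived.
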